7.2.1.4 Response Criteria

Evaluation of Target Lesions

Complete Response (CR)

Disappearance of all target lesions in the irradiated PTV, determined by two separate observations conducted not less than 4 weeks apart. Any pathological lymph nodes (whether target or non-target) must have reduction in short axis to <10 mm (the sum may not be “0” if there are target nodes). There can be no appearance of new lesions in irradiated PTV.

Partial Response (PR)

At least a 30% decrease in the sum of the longest diameter (LD) of target lesions in the irradiated PTV, taking as reference the baseline sum LD. There can be no appearance of new lesions in irradiated PTV.

Progressive Disease (PD)

At least a 20% increase in the sum of the SLD of target lesions, taking as reference the smallest sum SLD recorded since the treatment started and minimum 5 mm increase over the nadir, or the appearance of one or more new lesions in the irradiated PTV.

Stable Disease (SD)

Neither sufficient shrinkage to qualify for PR nor sufficient increase to qualify for PD, taking as reference the smallest sum LD since the treatment started.

Evaluation of Best Overall Response

The best overall response is the best response recorded from the start of the treatment until disease progression/recurrence (taking as reference for PD the smallest measurements recorded since the treatment started). The patient's best response assignment will depend on the achievement of both measurement and confirmation criteria.

Table 7.1 Response Criteria

Target Lesions	Non-Target Lesions	New Lesions	Overall Response	Best Response for this Category Also Requires
CR	CR	No	CR	> 4 weeks confirmation
CR	Non-CR/ Non-PD	No	PR	> 4 weeks confirmation
PR	Non-PD	No	PR	
SD	Non-PD	No	SD	documented at least once > 4 weeks from baseline
PD	Any	Yes or No	PD	no prior SD, PR or CR
Any	PD*	Yes or No	PD	
Any	Any	Yes	PD	

* In exceptional circumstances, unequivocal progression in non-target lesions may be accepted as disease progression. These circumstances should be discussed with the Principal Investigators.

Duration of Response

Duration of overall response

The duration of overall response is measured from the time measurement criteria are met for CR or PR (whichever is first recorded) until the first date that recurrent or PD is objectively

documented (taking as reference for PD the smallest measurements recorded since the treatment started).

The duration of overall CR is measured from the time measurement criteria are first met for CR until the first date that recurrent disease is objectively documented.

Duration of stable disease

Stable disease is measured from the start of the treatment until the criteria for progression are met, taking as reference the smallest measurements recorded since the treatment started.

Progression-Free Survival

Progression-free survival (PFS) is defined as the duration of time from start of treatment to time of progression or death due to any cause.

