therapy and for 24 months after completing therapy. Acceptable forms of primary contraception include the following: Combination hormonal contraceptives, subcutaneous hormonal implant, hormonal patch, hormonal contraceptives (levonorgestrel-releasing intrauterine system, medroxyprogesterone acetate depot), tubal sterilisation, vasectomy and intrauterine device (IUD). Acceptable forms of barrier contraception include the following: Any male condom (with spermicide) or diaphragm (with spermicide).

- Women should not breastfeed a baby while on this study, or for 24 months after completing therapy.
- Male patients must use condoms at all times, even after a vasectomy, during sexual intercourse with female partners of reproductive potential during treatment with vismodegib and for 2 months after the last dose to avoid exposing a pregnant partner and unborn fetus to vismodegib.

10. Life expectancy of <1 year

11. Patients with widespread superficial multifocal BCC who are considered unresectable due to breadth of involvement and do not have a single definable area of disease amenable to radiation therapy targeting.

Note: If an area including one or more lesions is definable for radiation therapy targeting, the patient may be eligible for treatment on study using the designated target lesion(s) identified by the investigator.

12. Uncontrolled intercurrent illness including, but not limited to, ongoing or active infection or psychiatric illness/social situations that would limit compliance with study requirements;

13. History of other disease, metabolic dysfunction, physical examination finding, or clinical laboratory finding giving reasonable suspicion of a disease or condition that contraindicates use of an investigational drug or that might affect interpretation of the results of the study or renders the patient at high risk for treatment complications

14. HIV-positive patients on combination antiretroviral therapy, because of the potential for pharmacokinetic interactions with vismodegib;

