7.2.1.2 Disease Parameters

Measurable disease

Measurable disease is defined as lesions (or tumors) that can be accurately measured in at least one dimension (longest diameter to be recorded) with a minimum size of 10mm by CT scan (irrespective of scanner type) and MRI (no less than double the slice thickness and a minimum of 10mm), 10mm caliper measurement by clinical exam (when superficial), and/or 20mm by chest X-ray (if clearly defined and surrounded by aerated lung).

Tumor measurements will be performed measuring the maximal diameter as the maximal extent of tumor plus any adjacent or underlying ulceration. All tumor measurements will be recorded in millimeters or decimal fractions of centimeters. Previously irradiated lesions are considered non-measurable except in cases of documented progression of the lesion since the completion of radiation therapy.

Target lesions

All measurable lesions up to a maximum of 5 lesions total (and a maximum of two lesions per organ) representative of all involved organs should be identified as target lesions and recorded and measured at baseline. Target lesions will be selected on the basis of their size (lesions with the longest diameter) and their suitability for accurate repeated measurements (either by imaging techniques or clinically). A sum of the longest diameter (LD) for all target lesions will be calculated and reported as the baseline sum LD. The baseline sum LD will be used as reference by which to characterize the objective tumor response.

Non-measurable disease

Non-measurable disease is all other lesions (or sites of disease), including small lesions (longest diameter <20 mm with conventional techniques or < 10 mm using spiral CT scan). Leptomeningeal disease, ascites, pleural or pericardial effusion, inflammatory breast disease, lymphangitic involvement of skin or lung, abdominal masses/abdominal organomegaly identified by physical exam that is not measurable by reproducible imaging techniques are all non-measurable.

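### Partial response compares target lesions inside the PTV with a baseline sum over all target lesions, so if targets outside the PTV make up at least 30% of that sum, an unchanged irradiated tumor counts as controlled

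*Combined protocol and SAP*

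**What the plan says.** **Target lesions and the reference.** Section 7.2.1.2 draws target lesions from "All measurable lesions up to a maximum of 5 lesions total (and a maximum of two lesions per organ) representative of all involved organs", choosing by size and suitability for repeat measurement. It then fixes a term: "A sum of the longest diameter (LD) for all target lesions will be calculated and reported as the baseline sum LD". Neither sentence mentions the PTV.

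**Partial response.** Section 7.2.1.4 sets the threshold at a 30% reduction, to be found "in the sum of the longest diameter (LD) of target lesions in the irradiated PTV, taking as reference the baseline sum LD". The follow-up sum is limited to the PTV. The reference is the term defined in 7.2.1.2.

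**Progression.** The growth rule in 7.2.1.4 is "At least a 20% increase in the sum of the SLD of target lesions", measured from the nadir and with a 5 mm minimum. It has no PTV limit. The alternative limb does: "or the appearance of one or more new lesions in the irradiated PTV".

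**Primary endpoint.** Sections 2.3.1 and 8.2 count complete or partial response at 12 months without progression inside the irradiated PTV. Section 8.5 counts CR or PR as control, and 8.5.1 judges failure inside the treated PTV.

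**Who may enter.** The note to exclusion 11 in 3.3.2 admits some patients with multifocal disease: "If an area including one or more lesions is definable for radiation therapy targeting", treatment may proceed on the target lesions that the investigator designates. Exclusion 5 foresees patients with several cutaneous BCCs, some of them not designated as targets.

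**The concern.** A percentage change means something only if both sums cover the same lesions. Here a lesion outside the PTV is counted in the reference and dropped at follow-up, so its whole diameter appears as shrinkage. The error runs towards success on the primary endpoint of a single-arm trial, where no control arm would carry the same error. Section 7 requires no central imaging review, so sites may also resolve the wording differently. The condition that there be no progression does not catch the problem, because an unchanged tumor has not progressed.

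The growth rule raises a lesser issue. The endpoint asks about progression inside the PTV, but the only sum defined for growth runs over all target lesions.

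**Working it through.** **1. The plan's own figure.** Inputs from 8.3.1: n = 24, null rate 0.60, alternative 0.80, one-sided 0.10, exact binomial test.
- Reject at 17 or more: P(X ≥ 17 | 0.60) = 0.192, above 0.10.
- Reject at 18 or more: P(X ≥ 18 | 0.60) = 0.096; power P(X ≥ 18 | 0.80) = 0.811.

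The stated 81% is reproduced, and the rule is 18 of 24.

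**2. The PR rule as written.** Let *a* be the baseline sum of targets inside the PTV, *b* the baseline sum of targets outside it, and *a₁* the in-PTV sum at follow-up.
- Scored change = a₁/(a + b) − 1.
- True in-PTV change = a₁/a − 1.
- For an unchanged tumor (a₁ = a), scored change = −b/(a + b). This reaches −30% when b is at least 30% of the baseline sum, that is b ≥ (0.3/0.7)a = 0.43a.

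| In-PTV baseline (mm) | Outside baseline (mm) | In-PTV follow-up (mm) | True change | Scored change | PR as written? |
|---|---|---|---|---|---|
| 30 | 0 | 30 | 0% | 0% | No |
| 30 | 10 | 30 | 0% | −25.0% | No |
| 50 | 20 | 50 | 0% | −28.6% | No |
| 20 | 10 | 20 | 0% | −33.3% | Yes |
| 30 | 20 | 30 | 0% | −40.0% | Yes |
| 30 | 20 | 35 | +16.7% | −30.0% | Yes |

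The 20 + 10 mm row uses the smallest sizes the protocol allows: a 20 mm qualifying lesion (3.3.1) and a 10 mm measurable superficial lesion (7.2.1.2).

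**3. The growth rule.** Take the baseline as the nadir and assume the lesion outside the PTV is 20 mm.
- *Growth diluted.* In-PTV 20 to 27 mm, outside stable at 20 mm. In-PTV sum: +7 mm, 7/20 = +35%, which would be progression. All-target sum: 40 to 47 mm, 7/40 = +17.5%, which is not. The PR rule gives 27/40 − 1 = −32.5%, which is PR.
- *Growth imported.* In-PTV 30 to 20 mm (−33%), outside 20 to 41 mm. All-target sum: 50 to 61 mm, 11/50 = +22%, which is progression on the sum in 7.2.1.4 although the irradiated tumor shrank.

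**4. Effect on the test.** One patient is 1/24 = 4.2 percentage points. The documents do not say how many patients would have targets outside the PTV, so the share *m* of true non-controls misscored as PR is an assumption. The control rate under the null becomes 0.60 + 0.40m.

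| Assumed m | Scored rate under the null | P(18 or more of 24) |
|---|---|---|
| 0% | 60% | 9.6% |
| 5% | 62% | 13.4% |
| 10% | 64% | 18.2% |
| 20% | 68% | 31.0% |

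**5. After the fix.** With the reference restricted to the same in-PTV lesions, an unchanged tumor scores a/a − 1 = 0% whatever *b* is. The figures in step 1 do not move.

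**The case against.** The strongest reply is that target lesions are meant to be the irradiated ones. The GTV is all known gross disease (5.2.5). PTV1 is to cover disease present after induction and areas involved on initial imaging (5.2.1, 5.2.2). The inclusion 1 note in 3.3.1 and exclusions 5 and 11 in 3.3.2 speak of targets that the investigator proposes or designates. Section 7.2 ties measurement to the primary site and involved regional nodes. If every target is irradiated, all the sums cover the same lesions and nothing is misscored.

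This narrows the point but does not remove it. No section requires every target to lie inside the PTV. Section 7.2.1.2, which builds the sum, starts from all measurable lesions. The PTV qualifier in the PR definition would be unnecessary if all targets were inside.

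Three stronger readings are tempting and should not be drawn:
- A reader might infer that any unchanged tumor can be scored PR. It cannot: a target must lie outside the PTV, and for an unchanged tumor such targets must reach 30% of the baseline sum.
- A reader might infer that contouring after induction, or the mention in 6.1.5 of a BCC in an untreated location, shows that baseline targets fall outside the PTV. PTV1 covers the pre-induction extent, and 6.1.5 concerns follow-up without saying that such a lesion was a baseline target.
- A reader might infer that regrowth outside the field makes a patient a primary failure, or that diluted growth inside it goes unseen. Sections 8.2 and 8.5.1 confine progression and failure to the PTV. Section 7.1 treats significant enlargement of a baseline cutaneous BCC as progression, and 7.3 has a separate rule based on the product of diameters. These cover part of the gap, but 8.2 refers to 7.2 for progression, and 7.2 gives no in-PTV sum.

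**Conclusion.** The PR rule is wrong as written, under a stated condition. In a patient with a target lesion outside the PTV, where such lesions make up at least 30% of the baseline sum, an unchanged irradiated tumor is scored PR and counted as local-regional control. The arithmetic follows from the plan's own definitions and needs no outside figure.

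How often this happens cannot be determined from the documents, and their planning and designation rules suggest that it is uncommon. The error probabilities above are therefore illustrations over an assumed range, not estimates. What can be said firmly is that the error favors success and that one patient can decide the result at 18 of 24. For progression, the finding is limited to a missing definition of the in-PTV sum. The sample size, the 0.096 type I error of the exact test and the 81% power stand as design figures. Severity: should fix.

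**What to change.** In 7.2.1.2 and 7.2.1.4, state that local-regional response, for both the primary endpoint and the 3-month response rate, uses a single lesion set:
- Targets are designated at baseline as the lesions planned for irradiation and are later confirmed to lie inside the PTV.
- The baseline, nadir and follow-up sums for CR, PR, SD and PD are all computed on that set.
- A designated target that proves to lie outside the final PTV is removed from both the baseline and the follow-up sums, and the removal is reported.
- Lesions outside the PTV are recorded separately, for example for PFS.

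Designating at baseline matters: a set chosen freely after contouring could depend on the response to induction. Removal should therefore follow only from the lesion's position relative to the PTV.

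The cost is protocol wording and one derived variable, since Section 7 already requires all baseline lesions to be reassessed. The PR rate may be slightly lower in patients with several lesions. The sample size and the 18 of 24 rule stay as they are.

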7.3 Assessment of Failure Patterns

Local or Regional Relapse

Relapse is defined as reappearance of tumor after complete response. If possible, relapse should be confirmed by biopsy.

Local or Regional Progression

Progression is defined as an estimated increase in the size of the tumor (product of the perpendicular diameters of the two largest dimensions) of greater than 20%, taking as reference the smallest value of all previous measurements or appearance of new areas of malignant disease. This should be compared to radiology reassessment done after the completion of radiation therapy.

Distant Metastasis Progression

Progression of a distant metastasis (e.g. lung, bone, brain, liver) is defined as an estimated increase in the size of the tumor (product of the perpendicular diameters of the two largest dimensions) of greater than 20%, taking as reference the smallest value of all previous measurements or appearance of new areas of malignant disease. This should be compared to radiology reassessment done after the completion of radiation therapy.

7.4 Evaluation of Safety

Analyses will be performed for all patients having received at least one dose of study drug. The study will use the CTCAE v4.0 for reporting of non-hematologic adverse events and modified criteria for hematologic adverse events. Safety assessments will consist of monitoring and reporting adverse events (AEs) and serious adverse events (SAEs) that are considered related to vismodegib, all events of death, and any study specific issue of concern.

The Principal Investigator at the UCSF Coordinating Center will hold the role of Study Chair. The Study Chair is responsible for the overall conduct of the study and for monitoring its safety and progress at all participating sites. The Study Chair is responsible for ensuring that all AEs and SAEs that are observed or reported during the study, are collected and reported to the FDA, appropriate IRB(s), and Genentech, Inc. in accordance with CFR 312.32 (IND Safety Reports).

The study period during which all AEs and SAEs must be reported begins after informed consent is obtained and initiation of study treatment and ends 1 year following the last administration of study treatment or study discontinuation/termination, whichever is earlier. After this period, investigators should only report SAEs that are attributed to prior study treatment.

7.5 Definitions of Adverse Events

7.5.1 Adverse Event

An adverse event (also known as an adverse experience) is defined as any untoward medical occurrence associated with the use of a drug in humans, whether or not considered drug related. More specifically, an adverse event (can be any unfavorable and unintended sign (e.g., an abnormal laboratory finding), symptom, or disease temporally associated with the use of a drug, without any judgment about causality. An adverse event can arise from any use of the drug (e.g., off-label use, use in combination with another drug) and from any route of administration, formulation, or dose, including an overdose.

This includes the following:

- AEs not previously observed in the subject that emerge during the protocol-specified AE reporting period, including signs or symptoms associated with locally advanced BCC of the head and neck that were not present prior to the AE reporting period.
- Complications that occur as a result of protocol-mandated interventions (e.g., invasive procedures such as cardiac catheterizations).

If applicable, AEs that occur prior to assignment of study treatment associated with medication washout, no treatment run-in, or other protocol-mandated intervention.

Preexisting medical conditions (other than the condition being studied) judged by the investigator to have worsened in severity or frequency or changed in character during the protocol-specified AE reporting period.

7.5.2 Adverse reaction

An adverse reaction is defined as any adverse event caused by the use of a drug. Adverse reactions are a subset of all suspected adverse reactions for which there is reason to conclude that the drug caused the event.

7.5.2.1 Suspected

A suspected adverse reaction is defined as any adverse event for which there is a reasonable possibility that the drug caused the adverse event. For the purposes of IND safety reporting, "reasonable possibility" indicates that there is evidence to suggest a causal relationship between the drug and the adverse event. A suspected adverse reaction implies a lesser degree of certainty about causality than an adverse reaction.

7.5.2.2 Unexpected

An adverse event or suspected adverse reaction is considered *unexpected* if it is not listed in the investigator brochure or package insert(s), or is not listed at the specificity or severity that has been observed, or, if an investigator brochure is not required or available, is not consistent with the risk information described in the general investigational plan or elsewhere in the current application.

"Unexpected," as used in this definition, also refers to adverse events or suspected adverse reactions that are mentioned in the investigator brochure as occurring with a class of drugs or as anticipated from the pharmacological properties of the drug, but are not specifically mentioned as occurring with the particular drug under investigation.

Adverse events that would be anticipated to occur as part of the disease process are considered *unexpected* for the purposes of reporting because they would not be listed in the investigator brochure. For example, a certain number of non-acute deaths in a cancer trial would be anticipated as an outcome of the underlying disease, but such deaths would generally not be listed as a suspected adverse reaction in the investigator brochure.

Some adverse events are listed in the Investigator Brochure as occurring with the same class of drugs, or as anticipated from the pharmacological properties of the drug, even though they have not been observed with the drug under investigation. Such events would be considered *unexpected* until they have been observed with the drug under investigation. For example, although angioedema is anticipated to occur in some patients exposed to drugs in the ACE inhibitor class and angioedema would be described in the investigator brochure as a class effect, the first case of angioedema observed with the drug under investigation should be considered *unexpected* for reporting purposes.

7.5.2.3 Serious

An adverse event or suspected adverse reaction is considered *serious* if, in the view of either the investigator or sponsor, it results in any of the following outcomes:

- Death
- Life-threatening adverse event
- Inpatient hospitalization or prolongation of existing hospitalization
- A persistent or significant incapacity or substantial disruption of the ability to conduct normal life function
- Congenital anomaly/birth defect

Important medical events that may not result in death, are life-threatening, or require hospitalization may be considered serious when, based upon appropriate medical judgment, they may jeopardize the patient or subject and may require medical or surgical intervention to prevent one of the outcomes listed in this definition. Examples of such medical events include allergic bronchospasm requiring intensive treatment in an emergency room or at home, blood dyscrasias or convulsions that do not result in inpatient hospitalization, or the development of drug dependency or drug abuse.

7.5.2.4 Life-threatening

An adverse event or suspected adverse reaction is considered *life-threatening* if, in the view of either the investigator or sponsor, its occurrence places the patient or subject at immediate risk of death. It does not include an adverse event or suspected adverse reaction that, had it occurred in a more severe form, might have caused death.

7.6 Recording of an Adverse Event

All grade 3 and above adverse events will be entered into OnCore[®], whether or not the event is believed to be associated with use of the study drug. Data about these events and their severity will be recorded using the NCI CTCAE v4.0.

The Investigator will assign attribution of the possible association of the event with use of the investigational drug, and this information will be entered into OnCore[®] using the classification system listed below:

Relationship	Attribution	Description
Unrelated to investigational drug/intervention	Unrelated	The AE is clearly NOT related to the intervention
	Unlikely	The AE is doubtfully related to the intervention
Related to investigational drug/intervention	Possible	The AE may be related to the intervention
	Probable	The AE is likely related to the intervention
	Definite	The AE is clearly related to the intervention

Signs or symptoms reported as adverse events will be graded and recorded by the Investigator according to the CTCAE v 4.0. When specific adverse events are not listed in the CTCAE v 4.0 they will be graded by the Investigator as *none, mild, moderate* or *severe* according to the following grades and definitions:

- Grade 0 No AE (or within normal limits)
- Grade 1 Mild; asymptomatic or mild symptoms; clinical or diagnostic observations only; intervention not indicated
- Grade 2 Moderate; minimal, local, or noninvasive intervention (e.g., packing, cautery) indicated; limiting age-appropriate instrumental activities of daily living (ADL)
- Grade 3: Severe or medically significant but not immediately life-threatening; hospitalization or prolongation of hospitalization indicated; disabling; limiting self-care ADL
- Grade 4: Life-threatening consequences; urgent intervention indicated
- Grade 5: Death related to AE

